 - “CSU diagnosis for \geq 6 months” changed to “CSU diagnosis for \geq 6 months (defined as onset of CSU with supporting documentation)”. Section 5.1 updated accordingly
 - “Subjects must be on H1-AH at only approved doses for treatment of CSU starting at Visit 1 (Day -28 to Day -14)” changed to “Subjects must be on H1-AH at only local label approved doses for treatment of CSU starting at Visit 1 (Day -28 to Day -14)” similar change is reflected in Section 4.1.1 and Section 5.1
 - “Any H2 antihistamine, Leukotriene Receptor Antagonist (LTRA) (montelukast or zafirlukast) or H1 antihistamines use at greater than approved dose after Visit 1” changed to “Any H2 antihistamine use or LTRA (montelukast or zafirlukast) after Visit 1 and any H1 antihistamine used as background medication at greater than local label approved doses after Visit 1” similar changes is reflected in Section 5.2
- **Section 4.1.1:** Added, “If a subject must switch to another background H1-AH (at approved dose) as a result of an AE, the subject will be considered to have remained on stable treatment.”
- **Section 5.1:** Included the word “local label” in Inclusion Criterion 4.
- **Section 5.2:** Added the term “background medication” and “local label” to Exclusion Criterion #10 in order to clarify that higher than approved doses of H1-AH as background medication are not allowed after Visit 1. This criterion does not apply to H1-AH taken as rescue medication which can be taken up to 4 times the approved dose.
- **Section 5.2:** Exclusion criterion 14 is amended to exclude hypersensitivity to all study drugs
- **Section 5.2:** Exclusion criterion 19, changed “History of” to “History of” and clarifies, that an INR > 1.5 (not INR > 1.5 ULN) is an exclusion criterion for this study.
- **Section 5.2:** Exclusion criterion 24, changed “basic contraception methods” to “Acceptable contraception methods” to be consistent with the CTFG guidelines for

contraception requirements in order to participate in the study. Section 4.5 and Section 7 updated accordingly.

- **Section 6.2.2: Table 6-2**

- Clarifies the term Routine as “more than 3 doses over a 5 day period” use of oral corticosteroids. Included IV/IM/IA corticosteroids as prohibited systemic routes of corticosteroid administration, with minimum required period without medication mentioned as 30 days prior to Visit 1.

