5.1 Inclusion criteria

Subjects eligible for inclusion in this study must meet **all** of the following criteria:

Main study

1. Signed informed consent must be obtained prior to participation in the study.
2. Male and female subjects ≥ 18 years of age at the time of screening
3. CSU diagnosis for ≥ 6 months (defined as onset of CSU with supporting documentation).
4. Diagnosis of CSU refractory to H1-AH at locally approved doses at the time of baseline (Visit 110, Day1), as defined by all of the following:
 - a. The presence of itch and hives for ≥ 6 consecutive weeks at any time prior to Visit 1 (Day -28 to Day -14) despite current use of non-sedating H1-AH (at locally approved doses) during this time period
 - b. UAS7 score (range 0-42) ≥ 16 and HSS7 (range 0-21) ≥ 8 during the 7 days prior to baseline (Visit 110, Day 1)
 - c. Subjects must be on H1-AH at only local label approved doses for treatment of CSU for starting at Visit 1 (Day -28 to Day -14)
5. Willing and able to complete a daily symptom eDiary for the duration of the study and adhere to the study visit schedules.
6. Subjects must not have had any missing eDiary entries in the 7 days prior to baseline (Day 1, Visit 110). i.e., 14 eDiary entries required. Re-screening may be considered only once.

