16. History of malignancy of any organ system within the past 5 years (except for basal cell carcinoma, actinic keratoses or Bowen disease (carcinoma in situ) that have been treated with no evidence of recurrence in the past 12 weeks; carcinoma in situ of the cervix or non-invasive malignant colon polyps that have been removed).
17. Presence of clinically significant cardiovascular (such as but not limited to myocardial infarction, unstable ischemic heart disease, New York Heart Association (NYHA) Class III/IV left ventricular failure, arrhythmia and uncontrolled hypertension within 12 months prior to Visit 1), neurological, psychiatric, metabolic, or other pathological conditions such as but not limited to cerebrovascular disease, neurodegenerative diseases, or other neurological disease, uncontrolled hypo- and hyperthyroidism and other autoimmune diseases, hypokalemia, hyperadrenergic state, or ophthalmologic disorder that could interfere with or compromise the safety of the subjects, interfere with evaluation or interpretation of the study results, or preclude completion of the study.
18. Medical examination or laboratory findings that suggest the possibility of decompensation of co-existing conditions for the duration of the study. Any items that are cause for uncertainty will be reviewed with the investigator.

19. History of, or current treatment for, hepatic disease including but not limited to acute or chronic hepatitis, cirrhosis or hepatic failure or Aspartate aminotransferase (AST)/Alanine aminotransferase (ALT) levels of more than 1.5 x upper limit of normal (ULN) and International Normalized Ratio (INR) of more than 1.5 at Visit 1.(see [Section 8.4.1](#))
20. History of renal disease or creatinine level above 1.5x ULN at Visit 1.
21. Platelets < 100,000/ μ L at Visit 1.
22. History of long QT syndrome or whose QT interval corrected by Fridericia's formula (QTcF) (Fridericia) measured at Visit 1 is prolonged (> 450 ms for males or > 460 ms for females) and confirmed by a central assessor (these subjects should not be re-screened).
23. Pregnant or nursing (lactating) women.
24. Women of child bearing potential, defined as all women physiologically capable of becoming pregnant, unless they are using basic (acceptable effective) methods of contraception for the duration of study (approx. 4 months, i.e. 5 half-lives, after last dose of ligelizumab). Acceptable contraception methods include:

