9.1 Discontinuation

9.1.1 Discontinuation of study treatment

Discontinuation of investigational treatment for a subject occurs when investigational treatment is stopped earlier than the protocol planned duration, and can be initiated by either the subject or the investigator.

The investigator must discontinue investigational treatment for a given subject if, he/she believes that continuation would negatively impact the subject's well-being.

Investigational treatment must be discontinued under the following circumstances :

- Subject decision
- Adverse events for which continued exposure to the study drug would be detrimental
- Abnormal renal laboratory results requiring discontinuation (see [Section 16.3](#) Appendix 3)
- Abnormal liver laboratory results requiring discontinuation (see [Section 16.2](#) Appendix 2)
- Platelets < 75,000/ μ L

- Pregnancy (See [Section 8.4.4](#) and [Section 10.1.4](#))
- Subject develops a medical condition that requires use of prohibited treatment as per [Section 6.2.2](#), or if subject exhibits a behavior of non-compliance regarding prohibited medications
- Subject received a live virus vaccination during the study
- Subject experiences an unexpected hypersensitivity reaction of grade 5, as defined by the World Allergy Organization Grading System ([Cox et al 2017](#)), see [Section 16.6](#) Appendix 6:
 - Lower or upper respiratory: Respiratory failure with or without loss of consciousness; or
 - Cardiovascular: Hypotension with or without loss of consciousness
- Emergency use of epinephrine due to anaphylactic or anaphylactoid reaction
- Any other protocol deviation that results in a significant risk to the subject's safety
- Any situation in which study participation might result in a safety risk to the subject
- If a subject uses rescue oral corticosteroids for CSU more than 3 doses in a 30 day period or more than 9 doses of in total after week 12 during the study period (including the follow-up period).

If discontinuation of investigational treatment occurs, the investigator should make a reasonable effort to understand the primary reason for the subject's premature discontinuation of study treatment and record this information. Always consider reasons which are related to safety and efficacy first.

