> 8 × ULN	
 • Discontinue the study treatment immediately • Hospitalize if clinically appropriate • Establish causality • Record the AE and contributing factors (eg, conmeds, med hx, lab) in the appropriate CRF 	ALT, AST, TBL, Alb, PT/INR, ALP and GGT until resolution ^c (frequency at investigator discretion)
> 3 × ULN and (TBL > 2 × ULN or INR > 1.5)	
 • Discontinue the study treatment immediately • Hospitalize, if clinically appropriate • Establish causality • Record the AE and contributing factors (eg, conmeds, med hx, lab) in the appropriate CRF 	ALT, AST, TBL, Alb, PT/INR, ALP and GGT until resolution ^c (frequency at investigator discretion)
> 5 to ≤ 8 × ULN	
 • Repeat LFT within 48 hours • If elevation persists, continue follow-up monitoring • If elevation persists for more than 2 weeks, discontinue the study drug • Establish causality • Record the AE and contributing factors (eg, conmeds, med hx, lab) in the appropriate CRF 	ALT, AST, TBL, Alb, PT/INR, ALP and GGT until resolution ^c (frequency at investigator discretion)
> 3 × ULN accompanied by symptoms ^b	
 • Discontinue the study treatment immediately • Hospitalize if clinically appropriate • Establish causality • Record the AE and contributing factors (eg, conmeds, med hx, lab) in the appropriate CRF 	ALT, AST, TBL, Alb, PT/INR, ALP and GGT until resolution ^c (frequency at investigator discretion)
> 3 to ≤ 5 × ULN (patient is asymptomatic)	
 • Repeat LFT within the next week • If elevation is confirmed, initiate close observation of the patient 	Investigator discretion Monitor LFT within 1 to 4 weeks
ALP (isolated)		

Criteria	Actions required	Follow-up monitoring
> 2 × ULN (in the absence of known bone pathology)	
 ● Repeat LFT within 48 hours ● If elevation persists, establish causality ● Record the AE and contributing factors (eg, conmeds, med hx, lab) in the appropriate CRF 	Investigator discretion Monitor LFT within 1 to 4 weeks or at next visit
TBL (isolated)		

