2.7.3 Laboratory data

All laboratory data will be listed by test group, subject, visit and laboratory test with abnormalities flag based on normal ranges. Shift tables for 2 groups of laboratory tests (hematology and serum chemistry) using the low/normal/high classification will be used to compare baseline to the worst on-treatment value. For the parameters with clinically notable abnormal criteria, newly occurred or worsening abnormality will also be summarized. A case is considered as a newly occurring abnormality if the value is not notable or missing at baseline but is notable thereafter during the study. A case is considered as a worsening abnormality if the value is notable at baseline and at least one post-baseline value during the study is worse than baseline.

The laboratory values below Lower Level of Quantification (LLOQ) or above Upper Level of Quantification (ULOQ) will be imputed as LLOQ or ULOQ in the summary tables, respectively. The numerical part of the reported result will be treated as the actual LLOQ or ULOQ. These laboratory values will be displayed in listings using the standard unit with the reported sign (“<” or “>”).

To evaluate potential drug-induced liver injury, newly occurring liver-enzyme abnormalities at any time post-baseline will also be summarized.

The notable criteria and abnormalities are described in section 5.3.

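### Exclusion criterion 19 joins the AST/ALT and INR limits with 'and', so read literally neither limit excludes alone and transaminases already at a stopping level can pass

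*Protocol*

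**What the plan says.** **Entry.** Criterion 19 (Protocol Section 5.2) has two limbs joined by 'or'. The first is a history of, or current treatment for, hepatic disease. The second is AST/ALT "levels of more than 1.5 x upper limit of normal (ULN) and International Normalized Ratio (INR) of more than 1.5" at Visit 1. Section 8.4.1, to which the criterion refers, allows a repeat draw during screening but sets no liver limit. The next criterion is built differently: "History of renal disease or creatinine level above 1.5x ULN at Visit 1".

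**Stopping.** In Table 16-2 (Protocol Section 16.2) the action for ALT or AST above 8 x ULN begins "Discontinue the study treatment immediately", with no INR condition. The same action applies above 3 x ULN with symptoms, and above 3 x ULN with bilirubin above 2 x ULN or INR above 1.5. For more than 5 and up to 8 x ULN the rule is "If elevation persists for more than 2 weeks, discontinue the study drug". Section 9.1.1 makes this binding by listing "Abnormal liver laboratory results requiring discontinuation" among the circumstances in which treatment must stop.

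**Intent.** The Amendment 01 rationale, describing its change to criterion 19, says that "an INR > 1.5 (not INR > 1.5 ULN) is an exclusion criterion for this study".

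**The concern.** An entry limit on transaminases should keep out subjects whose values would require treatment to stop. As worded, the AST/ALT limit works only when INR is also raised. A subject with markedly raised transaminases and normal coagulation meets no numeric exclusion and could receive a first dose at a level at which the same protocol orders discontinuation. An isolated INR above 1.5 passes in the same way.

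At stake is mainly the safety of that subject, in a trial whose primary objective is safety. A lesser issue is interpretation. A subject who enters with raised, fluctuating enzymes can later appear in a table of newly occurring liver abnormalities without much having changed.

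**Working it through.** The point is one of logic and the plan gives no figure to reproduce, so the check sets the entry rule beside the stopping rules.

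**1. The rules as logic**
- As written: excluded = hepatic history OR (AST/ALT > 1.5 x ULN AND INR > 1.5).
- Alternative: excluded = hepatic history OR AST/ALT > 1.5 x ULN OR INR > 1.5.
- Immediate stop (Table 16-2, ALT/AST rows): > 8 x ULN; or > 3 x ULN with bilirubin > 2 x ULN or INR > 1.5; or > 3 x ULN with symptoms.

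**2. Subjects without hepatic history**

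| ALT/AST (x ULN) | INR | Excluded as written | Excluded with 'or' | Immediate stop in Table 16-2 |
|---|---|---|---|---|
| 1.0 | 1.6 | no | yes | no |
| 1.6 | 1.0 | no | yes | no |
| 3.1 | 1.0 | no | yes | only with symptoms or bilirubin > 2 x ULN |
| 5.1 | 1.0 | no | yes | only with symptoms or bilirubin > 2 x ULN |
| 8.1 | 1.0 | no | yes | yes |
| 1.6 | 1.6 | yes | yes | no |
| 3.1 | 1.6 | yes | yes | yes |
| 8.1 | 1.6 | yes | yes | yes |

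The 8.1 / 1.0 row is the clear conflict. The 3.1 and 5.1 rows with INR 1.0 conflict when symptoms or raised bilirubin are present. With 'or', no subject who meets an ALT/AST-based immediate stop passes. Values between 1.5 and 3 x ULN without symptoms meet no ALT/AST stopping threshold, so they are not part of the safety point.

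**3. The 5 to 8 x ULN band**

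Screening is at "Visit 1 (Day -28 to Day -14"), and the study has no Day 0. The interval from Visit 1 to Day 1 is therefore 1 − (−14) − 1 = 14 days at the shortest and 1 − (−28) − 1 = 28 days at the longest. The stopping rule needs more than 14 days. A value in this band at Visit 1 that is still present at Visit 110 can therefore meet the rule on the day of first dose if Visit 1 fell on Day −28 to Day −15, but not on Day −14.

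**4. Effect on the tables**

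SAP Section 2.7.3 counts an abnormality as new only if it was not notable, or was missing, at baseline. SAP Section 5.4.1 grades ALT and AST in multiples of baseline when baseline is abnormal, starting at 1.5 x baseline. A stable elevation is therefore not counted as new. Table 5-1 (SAP Section 5.4.2) uses multiples of ULN. The fold-rise needed to cross a threshold newly is threshold / baseline:
- baseline at the 1.5 x ULN limit, to > 3 x ULN: 3 / 1.5 = 2.0;
- baseline 2.8 x ULN (assumed), to > 3 x ULN: 3 / 2.8 = 1.07;
- baseline 4.5 x ULN (assumed), to > 5 x ULN: 5 / 4.5 = 1.11.

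The last two are below 1.5, so Table 5-1 would count these rises and Section 5.4.1 would not.

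**The case against.** The strongest reply is that such a subject would hardly be dosed in practice.
- The hepatic-disease limb of criterion 19 needs no laboratory value, and a work-up at 8 x ULN could well produce a diagnosis.
- Criteria 17 and 18 let the investigator exclude on clinical grounds.
- Section 10.2.1 requires liver events to be considered during the study, and Table 16-1 makes ALT or AST above 5 x ULN such an event.
- Section 9.1.1 also stops treatment in any situation that might put the subject at risk.
- The amendment rationale shows what was meant, so this is a drafting slip and not a choice.

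This makes the event less likely, and many investigators would decline the subject. But each protection depends on a diagnosis, on judgement or on monitoring, and none restores the numeric limit. A conjunctive reading is also natural, because Table 16-2 uses 'and' in that sense for transaminases with bilirubin or INR. The evidence of intent supports the correction; it does not alter what a site is told to apply.

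Three further objections stand in part. The 5 to 8 x ULN argument needs the elevation to persist with no earlier action, and nothing says that the Visit 110 central result is available before dosing. The baselines of 2.8 and 4.5 x ULN are illustrative and mainly show that values near a cut-off cross it easily. The SAP's listings by subject and visit and its shift tables already reveal a raised baseline. It also treats a notable baseline as worsening when "at least one post-baseline value during the study is worse than baseline", without explaining how that fits with grading in multiples of baseline. For these reasons the analytical effect is put no higher than small.

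**Conclusion.** The concern holds on the text as it stands. With INR of 1.5 or below and no hepatic history, criterion 19 sets no upper limit on AST or ALT, and no other visible criterion sets one. A subject above 8 x ULN can pass it while meeting an unconditional immediate stop.

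The conclusion rests on a literal reading of 'and' and on the criteria visible in the public document. It does not claim that such a subject would get past the judgement-based criteria. No frequency is claimed, because the documents give no basis for one. The consequence for the analysis is small and confined mainly to the ULN-based counts in SAP Table 5-1. The correction is worth making because it concerns an operative safety threshold.

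**What to change.** Reword the laboratory limb of criterion 19 as: *AST or ALT of more than 1.5 x ULN, or INR of more than 1.5, at Visit 1*. Each limit then excludes alone, as the creatinine and platelet limits in criteria 20 and 21 already do.

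If enrolment has closed, review Visit 1 AST, ALT and INR for every dosed subject. Flag anyone above either limit and show the baseline value beside the SAP Table 5-1 counts.

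The cost is one word, by amendment or investigator letter. Both tests are already scheduled at Visit 1 (Tables 8-1 and 8-10). There may be a few more screen failures. The plan expects 81 − 65 = 16 failures, or 16/81 = 19.8%. Two more, an assumed number, would give 18/81 = 22.2%.

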6.1 Study treatment

6.1.1 Investigational drugs

Table 6-1 Investigational drug

Investigational Drug (Name and Strength)	Pharmaceutical Dosage Form	Route of Administration	Supply Type	Sponsor (global or local)
Ligelizumab 120 mg per 1 mL	Liquid in vial	sc	Open label subject packs; vials	Sponsor local

6.1.2 Additional study treatments

No other additional treatment beyond investigational treatment is requested for this trial. Subjects will continue to use their background medication H1-antihistamines at (locally approved doses) with a stable regimen during the study. For rescue medication, see [Section 6.2.3](#).

6.1.3 Treatment arms/group

All eligible subjects will be assigned at Visit 110 to ligelizumab group. Each subject will receive 1 injection of 1.0 mL ligelizumab every 4 weeks.

During the treatment period, study drug will be administered for 13 visits as per [Table 8-1](#).

6.1.4 Treatment duration

The planned duration of treatment is 52 weeks. Subjects may be discontinued from treatment earlier due to safety concerns or disease progression and/or at the discretion of the investigator or the subject. For subjects who in the opinion of the investigator are still deriving clinical benefit from QGE031, every effort will be made to continue provision of study treatment.

6.2 Other treatment(s)

6.2.1 Concomitant therapy

This study requires concurrent use of one second generation H1-AH at locally approved doses as background medication. Subjects must remain on a stable treatment regimen (type and dose of H1-AH) throughout the study.

If a subject must switch to another background H1-AH (at approved dose) as a result of an AE, the subject will be considered to have remained on stable treatment.

The investigator must instruct the subject to notify the study site about any new medications he/she takes after the subject was enrolled into the study. All medications, procedures and significant non-drug therapies (including physical therapy and blood transfusions) administered after the subject was enrolled into the study must be recorded on the appropriate electronic Case Report Forms (eCRF).

Each concomitant drug must be individually assessed against all exclusion criteria/prohibited medication. If in doubt the investigator should contact the Novartis medical monitor before entering a subject into treatment period or allowing a new medication to be started.

6.2.2 Prohibited medication

Use of the class of treatments displayed in [Table 6-2](#) is NOT allowed after start of screening. The minimum required period without prohibited treatment before Visit 1 is also listed in [Table 6-2](#). Each concomitant medication must be individually assessed against all exclusion criteria and the table below to see if it is allowed. If in doubt, the investigator should contact Novartis medical monitor or delegate before entering a subject to treatment period or allowing a new medication to be started.

Table 6-2 Prohibited medication

Medication	Minimum required period without medications
Omalizumab	4 months prior to Visit 1
Ligelizumab	No prior use allowed
Routine (more than 3 doses over a 5 day period) oral corticosteroids*	30 days prior to Visit 1
IV/IM/IA corticosteroids	30 days prior to Visit 1
Beta-blocker therapy	7 days prior to Visit 1
Leukotriene antagonists	Stop at Visit 1
H2-antihistamines	Stop at Visit 1
First generation H1-antihistamines	Stop at Visit 1
Hydroxychloroquine or chloroquine	30 days prior to Visit 1
Other immunosuppressive medication with or without known effect on CSU including but not limited to Methotrexate, cyclosporine A, cyclophosphamide, tacrolimus and mycophenolate mofetil	30 days prior to Visit 1
Intravenous immunoglobulin G	30 days prior to Visit 1

Medication	Minimum required period without medications
Plasmapheresis	30 days prior to Visit 1
Regular (daily or every other day) doxepin (oral)	14 days prior to Visit 1
Vaccination with inactivated viruses	48 hours prior to each dosing visit (i.e. Visit 110 to Visit 230)
Live attenuated vaccine	30 days prior to Visit 1
[REDACTED]	[REDACTED]

* Allowed only as rescue therapy only after Week12, on an as-needed basis for unbearable symptoms as per [Section 6.2.3](#). Other preparations of CS with limited systemic exposure for non-CSU indications can be used (e.g. Intra nasal or topical CS) as needed basis.

If the prohibited treatment was used during the study for any indication, the subject must discontinue use of the prohibited treatment if he/she wishes to continue in the study. If the subject received a live virus vaccination during the study, the subject must discontinue study treatment.

If a subject takes concomitant omalizumab (outside of study assigned tr [REDACTED] in the follow-up phase, the subject must discontinue from the study, in which case [REDACTED] ADA samples should not be collected at the End of Study (EoS) visit.

The table is not considered all inclusive. Medication should be assessed for adherence to the indication and other inclusion/exclusion criteria.

